5.1 Primary Outcome

- 5.1.1 The primary outcome measure is the percent change in mean cortical thickness (C.Th) of bones receiving 30 Gy or more at 3 months post SBRT, when compared to pre-SBRT cortical thickness

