6.3 Duration of Therapy

The hypothesized bone structural benefit of bisphosphonates with radiation is due to inhibition of early osteoclast activation within as little as 1 week of SBRT. In our preclinical studies, risedronate was only

given just prior to irradiation, and it was not given at all after irradiation was completed. Osteoclast activation only lasted for 1 week post irradiation in rodent models. In non-human primate models, the first follow up scans were performed at 2 months post irradiation, and these scans indicated maximal bone loss had already occurred which was persistent but not worsening on subsequent scans. For this reason, risedronate will be given only once prior to SBRT, at a dose of 150 mg, which is the recommended monthly dose in the setting of osteoporosis in post-menopausal females.

SBRT is given over the course of 3 to 10 treatments and generally this is performed over the course of 1.5 - 2 weeks. Radiation treatments are given every day or every other day Monday through Friday with the exclusion of the weekends or major holidays. In the absence of treatment delays due to adverse events, radiation treatments may continue until the planned treatment dose is reached or until one of the following criteria applies:

- Intercurrent illness that prevents further administration of treatment,
- Unacceptable adverse event(s)
- Patient decides to withdraw from the study

General or specific changes in the patient's condition render the patient unacceptable for further treatment in the judgment of the investigator.

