6.4 Duration of Follow-up

Follow-up for serious adverse events and mortality after the single dose of 150 mg of risedronate or placebo is administered will take place during the routine clinic visits during radiation treatment. Radiation treatments will occur within 1 – 3 weeks of taking the study drug. The 30 day follow-up window that is part of mandatory DSMC-SAE reporting will be considered 30 days from the end of all treatments of radiation. This visit can be either a phone call or a visit in person to review adverse events and may be conducted and documented in the medical record by either research study staff RNs or the treating physician. A window of +/- 7 business days is allowed for the 30 day followup assessment.

Specific toxicity related to radiation pneumonitis, radiation fibrosis, and chest wall pain will be collected at each followup point as per appendices K – M.

Patients removed from study for unacceptable adverse events will be followed until resolution or stabilization of the adverse event.

Patients will be followed for a minimum of 3 months for assessment of the primary objective.

Patients will be ideally followed in total for 12 months after completion of radiation therapy for the purposes of this study.

In the event that patients develop progressive disease or a new cancer, requiring additional chemotherapy they will be withdrawn from further study directed followup. In these situations, the followup schedules and imaging become dramatically different from what is directed on this protocol. Additionally further systemic chemotherapy treatments can heavily alter bone density/cortical thickness. As such, if patients develop new disease requiring additional systemic chemotherapy treatment outside of their initial SBRT, they will be withdrawn from study for further follow ups/study directed imaging. Any data that was collected prior to study withdrawal will still be used in analysis. **Immunotherapy or**

hormonal therapy for breast or prostate cancer will not be considered reasons for withdrawal.
Cryoablation or radiofrequency ablation will not be considered a reason for withdrawal from study.

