6.6 Study Calendar

	Baseline Prior to SBRT	Dosing (7- 21 days before SBRT)	During SBRT	1 month Post SBRT	3 ^f months post SBRT	6 ^f months Post SBRT	9 ^f months Post SBRT	12 ^f months Post SBRT
Informed consent	X							
Demographics Medical history History of diabetes Physical exam Performance status Vital signs Height, Weight, M ²		X						
Current Medications list	X				X			
Current or prior use of rank ligand inhibitors, bisphosphonates, and steroids with dates of use and dose as per Appendix G. ^h	X				X	X	X	X
CT chest with or without contrast	X ^a				X	X	X	X
Risedronate or placebo		X ^c						
Urine sample ^d	X				X	X	X	X
Serum Calcium EGFR Serum Creatinine Pregnancy test ^b		X						
Adverse event evaluation (Appendix E)					X			
Specific Radiation Related Chest wall Toxicity (Appendix K)				X ^e	X	X	X	X
Follow up phone call for assessment of adverse events without imaging (Appendix F)				X				
Fracture Incidence (Appendix Q)	X				X	X	X	X
Radiation Treatment Details (Appendix N)			X ^g					

^a Pre-SBRT CT chest scan will be the treatment planning scan. Fracture incidence will be assessed on CT scans

^b Urine pregnancy test (women of childbearing potential) performed within 1 week of treatment planning simulation for radiation.

^c Given once at 7 – 21 days prior to initiation of SBRT

^d For urine sample pick-up and transport, call [name] at [contact] (mobile), [contact] (office). If not available, call [name] at [contact] (mobile).

^e At the 30-Day time point this can be collected over the phone

^f Every 3 month follow-up, and CT imaging will have a window of +/- 8 wks

^g Appendix N may be completed during SBRT but should be completed within 12 weeks of completing SBRT

All pre-study activities must be completed within 12 weeks of the start of study drug including labs

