7.0 Measurement of Effect

7.1 Cortical Thickness Mapping Approach and Radiation Dose Mapping

We will utilize our published novel method of cortical thickness mapping as outlined below.

Ribcage and vertebral cortical thickness mapping will be performed for each patient utilizing the CT scan at time of “simulation” or treatment planning/mapping and routine standard of care follow-up imaging at 3 months, 6 months, 9 months, and 12 months, which would be performed regardless of inclusion on this study.

The bony anatomy of the thorax will be segmented for each CT scan using automated thresholding techniques and manual editing in Mimics (v16.0 Materialise, Leuven, Belgium) for Windows. Individual contours of the entire ribs and vertebral bodies from cervical (C) level C7 through thoracic (T) level T12 will be constructed in treatment planning software.

These contours will be utilized to construct 3D surfaces containing over 100,000 vertices throughout the bony thorax using Stradwin software (v5.0 Cambridge University, Cambridge, England) for Windows.

Our unique cortical bone mapping algorithm relies on a global cortical density measurement, which is factored into a piecewise defined Heaviside step function derived from the convolution of the in-plane and out-of-plane point spread functions (PSFs) of each CT scan.

The global cortical bone density for each CT scan will be determined by collecting density measurements at each vertex. The CT values along a 12 mm line normal to the cortical surface at each of the approximately 50,000 vertices of the 3D rib surfaces will be obtained and applied to the validated Ct.Th estimation model constrained by the cortical density and out-of-plane blur.

Cortical thickness maps will be constructed using the pre-SBRT planning CT scan and 3 month post-SBRT follow up CT scan for each treated patient for evaluation of the primary objective. We will similarly perform this analysis at the 6 months, 9 months, and 12 months post SBRT time points for evaluation of secondary objectives.

The received radiation doses to the surface of the ribcage at each vertex will be obtained in MIM and then registered to the corresponding Ct.Th map using iterative closest point (ICP) registration in MATLAB (v2014a, MathWorks, Natick, MA). Each rib will be subdivided into evenly spaced cylindrical subsections (30 subsections per rib) along its centerline using a custom MATLAB algorithm.

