7.3 Detection of Rib/Vertebral Body fractures

The incidence of rib and or vertebral fractures within the radiation treatment field within the 50% isodose line will be collected from standard follow-up CT imaging at 3, 6, 9, and 12 months post SBRT.

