11.0 Statistical Considerations

11.1 Analysis of Primary Objective

The percent change in mean cortical thickness within regions receiving 30 Gy or more will be calculated from time of the treatment planning CT scan to 3 months post SBRT. This % change will be compared between the patients receiving risedronate and those receiving placebo.

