11.4 Power and Sample Size

Per analysis of our retrospective human data and preclinical data, we estimate that the mean cortical thickness for both cases and controls pre SBRT will be approximately 1.35 mm. At 3 months, in the absence of any treatment, we estimate approximately 16.7% loss of cortical thickness to bones to 1.13 mm (thus resulting in a mean change of 0.22 mm in controls) within the treatment field in regions of bone receiving ≥ 30 Gy. Conservatively, if risedronate use limits loss of cortical thickness by at least half on a percentage scale (i.e., expected cortical thickness at 3 months in treatment group 8.4% lower, or 1.24 mm, corresponding to an expected mean change in treatment group of 0.11 mm), and assuming a standard deviation of delta cortical thickness in both treatment and control patients of 0.20,⁴ then with a power of 0.80 and a one-tailed alpha of 0.05, we anticipate that we will need 42 patients per group to achieve desired power to illustrate significantly higher preservation of cortical thickness at 3 months post SBRT.

There is no human data to accurately estimate how significantly risedronate will limit bone loss following SBRT, however in our pre-clinical rodent models, cortical thickness was preserved in all mice receiving risedronate and in two mice cortical thickness increased. We have no mechanistic reason to suspect that risedronate would cause increased bone loss and therefore are utilizing a one-tailed alpha in our calculations.

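### Do the overlapping ±8-week CT windows leave the 3-month primary scan undefined?

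*Combined protocol and SAP*

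**What the plan says.** Footnote f of the Study Calendar (section 6.6) covers the 3-, 6-, 9- and 12-month columns: "Every 3 month follow-up, and CT imaging will have a window of +/- 8 wks". Section 5.1 defines the primary outcome as the percent change in mean cortical thickness "at 3 months post SBRT, when compared to pre-SBRT cortical thickness". Section 11.1 has it "calculated from time of the treatment planning CT scan to 3 months post SBRT". Section 7.1 takes it from the planning scan and the "3 month post-SBRT follow up CT scan for each treated patient for evaluation of the primary objective". Fracture data, under section 7.3, "will be collected from standard follow-up CT imaging at 3, 6, 9, and 12 months post SBRT".

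These sections name time points without day ranges. None says which visit owns a scan that fits two windows, or which scan to use when two fall in one window. Appendices O (cortical thickness) and Q (fractures) are listed in the contents, but their forms are not in the text reviewed, so a rule there cannot be excluded.

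On the time course of bone loss, section 6.3 reports that primates were first scanned 2 months after irradiation and that "these scans indicated maximal bone loss had already occurred which was persistent but not worsening on subsequent scans".

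**The concern.** A symmetric window that is wider than half the visit spacing must overlap its neighbours. A first CT at week 19 lies inside both the 3-month and the 6-month window. Read one way it supplies the primary endpoint; read the other way the primary value is missing. The repeated measures analysis in section 11.2.1 also needs one visit label per scan.

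A second worry is timing spread. A 3-month value read at week 5 may not measure the same thing as one read at week 21. If bone loss is still developing at the early end, the difference between arms shrinks, the variance grows and power falls.

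**Working it through.** **The plan's own sample size.** Section 11.4 gives a difference of 0.22 − 0.11 = 0.11 mm, an SD of 0.20, one-sided alpha 0.05 and power 0.80. The standardised difference is 0.11 / 0.20 = 0.55. A two-sample t-test needs 41.57 per group, rounded up to the plan's 42. Power at 42 is 0.804.

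**Windows.** One month = 365.25 / 12 / 7 = 4.348 weeks, so the spacing is 3 × 4.348 = 13.04 weeks and half of that is 6.52 weeks.

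| Visit | Target week | Window (±8 weeks) |
|---|---|---|
| 3 months | 13.04 | 5.0 to 21.0 |
| 6 months | 26.09 | 18.1 to 34.1 |
| 9 months | 39.13 | 31.1 to 47.1 |
| 12 months | 52.18 | 44.2 to 60.2 |

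Each overlap is 16 − 13.04 = 2.96 weeks. With 4-week months it would be 4 weeks, so the conversion does not decide the matter. The midpoint between the 3- and 6-month targets is 19.6 weeks.

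**How many scans are affected.** The documents give no scan-date distribution. The assumption here is dates normal around week 13.04, truncated at ±8 weeks, with an even spread as the extreme. Counts assume that all 84 patients have a 3-month scan.

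| Assumed spread | In overlap (after week 18.1) | Past midpoint (after week 19.6) | Before 2 months (week 8.7) |
|---|---|---|---|
| SD 2 weeks | 0.6% (0.5 of 84) | 0.05% (0.04 of 84) | 1.5% |
| SD 3 weeks | 4.3% (3.6) | 1.1% (0.9) | 7.0% |
| SD 4 weeks | 8.5% (7.1) | 3.0% (2.5) | 12.1% |
| Even | 18.5% (15.5) | 9.2% (7.8) | 22.8% |

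A nearest-target rule would move only the scans past the midpoint.

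**Power.** Let p be the share of scans before week 8.7 and f the fraction of the eventual loss that they show. The difference becomes 0.11 × [1 − p(1 − f)]. The variance in each arm becomes 0.20² + p(1 − p)[(1 − f) × loss]², with loss 0.22 mm in controls and 0.11 mm on risedronate; the two variances are averaged. For SD 4 and f = 0.5, the difference is 0.11 × (1 − 0.1213 × 0.5) = 0.103, the SD is 0.202 and power is 0.75.

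| Assumed spread | f = 0.5 | f = 0.8 | f = 1 |
|---|---|---|---|
| SD 2 weeks | 0.80 | 0.80 | 0.80 |
| SD 3 weeks | 0.77 | 0.79 | 0.80 |
| SD 4 weeks | 0.75 | 0.79 | 0.80 |
| Even | 0.70 | 0.77 | 0.80 |

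The result depends on f, for which the documents give no human value. Section 6.3 leans towards a high one: osteoclast activation lasted one week in rodents, and 2 months was the first primate scan, so it is the latest time by which loss was complete. Section 11.4 also rests partly on retrospective human data, "assuming a standard deviation of delta cortical thickness in both treatment and control patients of 0.20". That SD may already include some scan-timing spread, in which case the added variance counts it twice.

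**The case for a change.** The best case for a change does not need the power figures. The overlap is certain, it touches the primary endpoint, and the choice of scan should be settled before unblinding. Because the CTs are routine care, the study does not set their dates. The animal evidence does not cover weeks 5 to 8.7 in humans. The hardest example is a patient scanned at weeks 6 and 19, on a normal 13-week interval. Both scans lie in the 3-month window, and week 19 is the closer to target (5.96 against 7.04 weeks away). Fractures raise a related point: sections 2.2.3 and 5.2.3 limit the endpoint to 12 months, yet the 12-month CT may fall at week 60.

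What stands is that no written rule was found, and that one sentence in the SAP would do no harm. The rest is weaker. Visits occur in order, each with its own CT, urine sample, pain grading and fracture assessment. The week-6 scan is therefore the 3-month visit and the week-19 scan the 6-month visit, which its window allows. A lone first scan at week 19 is the 3-month visit. Section 6.4 supplies the time origin: "Patients will be ideally followed in total for 12 months after completion of radiation therapy".

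A more elaborate rule set brings its own problems. A nearest-target rule without a lower limit could let a stray CT at week 4 displace a permitted one at week 20. Asking for an extra 6-month CT would conflict with section 8.1, which rules out scans beyond standard of care. Counting every fracture seen on a late 12-month CT would stretch an endpoint defined as 12 months.

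**Conclusion.** No change follows. This is a gap in detail that analysts would fill sensibly: label scans by visit in sequence, use each scan once, and keep a first in-window CT as the primary value. Writing that down would give the same primary data set in all but a handful of cases. With a scan-date SD of 2 to 3 weeks, about 0 to 1 of 84 scans lie past the midpoint; with an even spread, about 8 do.

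The width of the window is a fair trade-off for a trial that relies on routine imaging, since a tighter limit would turn permitted scans into missing primary values. An assignment rule that keeps ±8 weeks would not remove early scans, so it would not recover any power lost to them. That loss is hypothetical: power stays at 0.80 if loss is complete by the earliest scans, is 0.77 to 0.80 if early scans show 80% of it, and is 0.70 to 0.80 at 50%, across the assumed spreads. Randomisation, and blinding of investigators until every patient has finished 12 months (section 10.0), make a difference in scan timing between arms unlikely.

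The conclusion rests on most CTs falling reasonably near their targets, and on early completion of bone loss carrying over at least roughly from the animal data in section 6.3.

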7.0 Measurement of Effect

7.1 Cortical Thickness Mapping Approach and Radiation Dose Mapping

We will utilize our published novel method of cortical thickness mapping as outlined below.

Ribcage and vertebral cortical thickness mapping will be performed for each patient utilizing the CT scan at time of “simulation” or treatment planning/mapping and routine standard of care follow-up imaging at 3 months, 6 months, 9 months, and 12 months, which would be performed regardless of inclusion on this study.

The bony anatomy of the thorax will be segmented for each CT scan using automated thresholding techniques and manual editing in Mimics (v16.0 Materialise, Leuven, Belgium) for Windows. Individual contours of the entire ribs and vertebral bodies from cervical (C) level C7 through thoracic (T) level T12 will be constructed in treatment planning software.

These contours will be utilized to construct 3D surfaces containing over 100,000 vertices throughout the bony thorax using Stradwin software (v5.0 Cambridge University, Cambridge, England) for Windows.

Our unique cortical bone mapping algorithm relies on a global cortical density measurement, which is factored into a piecewise defined Heaviside step function derived from the convolution of the in-plane and out-of-plane point spread functions (PSFs) of each CT scan.

The global cortical bone density for each CT scan will be determined by collecting density measurements at each vertex. The CT values along a 12 mm line normal to the cortical surface at each of the approximately 50,000 vertices of the 3D rib surfaces will be obtained and applied to the validated Ct.Th estimation model constrained by the cortical density and out-of-plane blur.

Cortical thickness maps will be constructed using the pre-SBRT planning CT scan and 3 month post-SBRT follow up CT scan for each treated patient for evaluation of the primary objective. We will similarly perform this analysis at the 6 months, 9 months, and 12 months post SBRT time points for evaluation of secondary objectives.

The received radiation doses to the surface of the ribcage at each vertex will be obtained in MIM and then registered to the corresponding Ct.Th map using iterative closest point (ICP) registration in MATLAB (v2014a, MathWorks, Natick, MA). Each rib will be subdivided into evenly spaced cylindrical subsections (30 subsections per rib) along its centerline using a custom MATLAB algorithm.

Rib vertices from the pre-SBRT CT scans will be spatially aligned with the post-SBRT CT in 3D Slicer (v 3.6, <http://www.slicer.org>) in Windows to define homologous rib subsections on the post-SBRT CT scan. A rigid transform consisting of translation and rotation operations will be computed and applied to align the pre- and post- treatment ribcage surfaces. A series of approximately twenty-five points will be manually selected on the ribcage surface to derive each transform. An affine transform will then be computed using an iterative closest point (ICP) algorithm and applied to the transformed ribcage surface to account for geometric interscan variation. The mean dose and Ct.Th for each homologous rib region will be calculated from the Ct.Th and dose measurements at all vertices within that region.

Bone within the treatment field (within the 50% isodose line) will be segmented into homologous regions receiving dose at 10 Gy intervals, of 0-10 Gy, > 10 – 20Gy, >20 – 30 Gy, > 30 – 40 Gy, and >40 Gy, and in each region the mean cortical thickness will be calculated. The % change in cortical thickness will be compared in each region between patients who received risedronate and those who received placebo.

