2.2 Secondary Objective(s)

- 2.2.1 In addition to the primary objective, we will further analyze the remaining routine follow-up chest CT scans, for mean cortical thickness change in regions of bone that received 0 – 10 Gy, >10 – 20 Gy, > 20 – 30 Gy, > 30 – 40 Gy, and > 40 Gy at all time points including 3 months, 6 months, 9 months, and 12 months. These scans are standard of care and would be performed regardless of inclusion on this trial. This will allow us to determine the potential persistence of effects from SBRT and bisphosphonate use.
- 2.2.2 We will assess and compare the incidence and grade (per modified CTCAE v.5) of radiation induced chest wall pain within the radiation treatment portal (within the 50% isodose line) at time of each routine follow up visit (3 months, 6 months, 9 months, and 12 months post SBRT). The purpose of utilizing a placebo and double-blind design is that chest wall pain is a subjective finding. Furthermore, it is unclear if chest wall pain from radiation is directly due to bone damage, nerve damage, muscle irritation, or a combination of all of these factors. The use of placebo will help us reduce the potential for bias in pain assessment.
- 2.2.3 We will assess and compare the incidence of rib and vertebral fractures (as noted on CT imaging) that occur within 12 months of irradiation and are within the radiation treatment field. The radiation treatment field will be defined as within the 50% isodose line.
- 2.2.4 The urine concentration of an osteoclast-specific biomarker, urinary N-telopeptide (NTX) indicating osteoclast activity will be assessed prior to SBRT and at each routine follow up visit (at 3 months, 6 months, 9 months, and 12 months post SBRT).

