5.2 Secondary Outcomes

- 5.2.1 The change in mean C.Th of bones will be assessed in regions of bone that received 0 – 10 Gy, >10 – 20 Gy, > 20 – 30 Gy, > 30 – 40 Gy, and > 40 Gy at all time points including 3 months, 6 months, 9 months, and 12 months.
- 5.2.2 Chest wall pain incidence and grade will be collected as per modified CTCAE v. 5 within the within the 50% isodose line. Appendix K
- 5.2.3 Incidence of rib and vertebral fractures (as noted on CT imaging) that occur within 12 months of irradiation and are within the within 50% isodose line.
- 5.2.4 The urine concentration of an osteoclast-specific biomarker, urinary N-telopeptide (U-NTX) indicating osteoclastic activity will be assessed prior to SBRT and at each routine follow up visit (at 3 months, 6 months, 9 months, and 12 months post SBRT).

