6.0 Treatment Plan

6.1 Treatment Administration

Treatment will be administered on an outpatient basis.

Reported adverse events and potential risks of SBRT and risedronate are described in Section 8.

REGIMENT DESCRIPTION			
Agent	Dose	Route	Schedule
Risedronate	150 mg	Oral	Given once 7 – 21 days prior to initiation of SBRT
Matching Placebo	N/A	Oral	Given once 7 – 21 days prior to initiation of SBRT

Standard of care radiation therapy with SBRT will be given over the course of 3 – 10 fractions to a total dose of 50 – 60 Gy at the discretion of the treating radiation oncologist. Specific dose fractionations between 3 – 10 fractions and constraints will be at the discretion of the treating radiation oncologist and may be prescribed every day or every other day. Respecting the following constraints are encouraged but meeting these constraints is not required for inclusion in the study. In many cases meeting the rib constraint will not be possible.

Treatment planning will be performed utilizing a vac lock or body fix bag and optional abdominal compression at the discretion of the treating radiation oncologist. Planning CT chest may be performed with or without contrast at the discretion of the treating radiation oncologist. Utilization of motion management with 4D cinematic CT or a slow scan is required for determination of the internal target volume (ITV). Clinical treatment volume (CTV) creation is not necessary and is not our standard treatment paradigm with SBRT for peripheral lung tumors. The planning target volume (PTV) is generally created as a 0.5 cm expansion from the ITV, however the exact dimensions of this expansion are at the discretion of the treating radiation oncologist.

The following are encouraged but not required dose constraints.

Three Fractions

Serial Tissue	Volume	Volume Max (Gy)	Max Point Dose (Gy)	Endpoint (≥Grade 3)
Spinal Cord	<0.5 cc	18 Gy (6 Gy/fx)	22 Gy (7.33 Gy/fx)	myelitis
Cauda Equina	<5 cc	21.9 Gy (7.3 Gy/fx)	24 Gy (8 Gy/fx)	neuritis
Sacral Plexus	<3 cc	22.5 Gy (7.5 Gy/fx)	24 Gy (8 Gy/fx)	neuropathy
Esophagus*	<5 cc	21 Gy (7 Gy/fx)	27 Gy (9 Gy/fx)	stenosis/fistula
Ipsilateral Brachial Plexus	<3 cc	22.5 Gy (7.5 Gy/fx)	24 Gy (8 Gy/fx)	neuropathy
Heart/Pericardium	<15 cc	24 Gy (8 Gy/fx)	30 Gy (10 Gy/fx)	pericarditis
Great vessels	<10 cc	39 Gy (13 Gy/fx)	45 Gy (15 Gy/fx)	aneurysm
Trachea and	<4 cc	15 Gy (5 Gy/fx)	30 Gy (10 Gy/fx)	stenosis/fistula
Ipsilateral Bronchus*				

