11.2 Analysis of Secondary Objectives

11.2.1

Percent change in cortical thickness across all time points

The percent change in mean cortical thicknesses from baseline will be assessed at 3 months, 6 months, 9 months, and 12 months post SBRT separately within regions of bone receiving 0 – 10 Gy, >10 – 20 Gy, > 30 – 40 Gy, and >40Gy. These outcomes will be compared using repeated measures analysis of variance (ANOVA).

11.2.2

Incidence and grade of chest wall pain

The incidence and grade of chest wall pain occurring inside the 50% isodose line will be collected and reported per modified CTCAE v5.0 (Appendix K) at 3 months, 6 months, 9 months, and 12 months post SBRT for all patients. Results will be compared between patients receiving placebo or risedronate. The incidence of G3 or greater chest wall pain will also be correlated with the volume of chest wall receiving at least 30 Gy or greater. The chest wall contour is defined as a 2 cm expansion from lung, from the costovertebral angle to the sternum.

11.2.3

Incidence of rib or vertebral fractures

The incidence of rib or vertebral fractures within the treatment field occurring at any time during the entire course of the study (12 months), will be reported and compared between patients receiving placebo or risedronate.

11.2.4

Urinary excretion of N-telopeptide (NTX)

The concentration of urinary NTX will be assessed at each time point from baseline to the conclusion of the study at 12 months. Results will be directly compared in each group.

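### Section 7.1 bands only bone inside the 50% isodose line, which all but empties the two lowest dose bands promised in 2.2.1, and 11.2.1 drops the >20–30 Gy band

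*Combined protocol and SAP*

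**What the plan says.** Four sections of the combined protocol and SAP describe the dose-banded cortical thickness analysis.

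- **2.2.1 (objective)** asks "for mean cortical thickness change in regions of bone that received 0 – 10 Gy" and in four further bands (>10–20, >20–30, >30–40 and >40 Gy), at 3, 6, 9 and 12 months. No isodose limit is given.
- **5.2.1 (outcome)** repeats the five bands, again without a limit: "The change in mean C.Th of bones will be assessed in regions of bone that received 0 – 10 Gy".
- **7.1 (measurement)** lists the same five bands but limits the bone that enters them: "Bone within the treatment field (within the 50% isodose line) will be segmented into homologous regions receiving dose at 10 Gy intervals".
- **11.2.1 (analysis)** has no isodose limit but names only four bands: "within regions of bone receiving 0 – 10 Gy, >10 – 20 Gy, > 30 – 40 Gy, and >40Gy". The >20–30 Gy band is missing.

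Section 6.1 gives SBRT "to a total dose of 50 – 60 Gy at the discretion of the treating radiation oncologist". Section 2.2.3 defines the treatment field, for fractures, by the same 50% line, and the line is also used for chest wall pain. Section 7.1 maps far more bone than lies inside it: "Individual contours of the entire ribs and vertebral bodies from cervical (C) level C7 through thoracic (T) level T12 will be constructed", and "The received radiation doses to the surface of the ribcage at each vertex will be obtained in MIM".

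**The concern.** The sentence in 7.1 works against itself. A region bounded below by half the total dose cannot supply bone at the low doses the sentence goes on to list, apart from edge cases. It also contradicts the objective, the outcome and the analysis section, none of which limits the bone.

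The set of reported results therefore depends on which section the analyst follows. One analyst would report thickness change in low-dose bone and another would have nothing to report there. If >20–30 Gy were analysed, it could be the whole band or a truncated one. Left open until the arms are known, that choice could be influenced by the results.

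**Working it through.** **The plan's own design figure.** Section 11.4 assumes a difference of 0.22 − 0.11 = 0.11 mm, an SD of 0.20 mm, one-sided alpha 0.05 and power 0.80. The standardised difference is 0.11 / 0.20 = 0.55. A two-sample t-test then needs 41.57, rounded up to 42 per group, as stated. It does not depend on the banding.

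**Position of the 50% line.** The documents do not say whether 50% refers to the prescribed or the maximum dose. Taking the prescribed total dose D from 6.1, line = 0.5 × D, and the part of >20–30 Gy left inside it is 30 − line.

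| D (Gy) | Line (Gy) | 0–10 | >10–20 | >20–30 | >30–40 and >40 |
|---|---|---|---|---|---|
| 50 | 25 | none | none | 25–30 (5 Gy wide) | whole |
| 55 | 27.5 | none | none | 27.5–30 (2.5 Gy wide) | whole |
| 60 | 30 | none | none | edge value only | whole |

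**Dose at which the low bands would be reached.** The line meets the top of >10–20 Gy at 20 / 0.5 = 40 Gy, and the top of 0–10 Gy at 10 / 0.5 = 20 Gy. Both are below the stated minimum of 50 Gy.

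**Two exceptions.**

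1. *Courses stopped early (6.3).* If the line follows the delivered dose, >10–20 Gy opens only at 40 Gy or less delivered, and 0–10 Gy only at 20 Gy or less.
2. *Rib subsections that straddle the line.* Under 7.1, "Each rib will be subdivided into evenly spaced cylindrical subsections (30 subsections per rib) along its centerline", and dose is averaged over each region. To enter >10–20 Gy, a subsection's mean must be at least 25 − 20 = 5 to 30 − 20 = 10 Gy below the line. To enter 0–10 Gy, it must be at least 25 − 10 = 15 to 30 − 10 = 20 Gy below. The documents do not say whether straddling subsections count as inside.

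**What each reading delivers, over four time points.**

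- 2.2.1 and 5.2.1: 5 bands, 5 × 4 = 20 band-by-time results.
- 11.2.1 alone: 4 bands, 4 × 4 = 16.
- 7.1 alone: 2 whole bands plus a truncated >20–30 Gy.
- 7.1 and 11.2.1 together: 2 bands (>30–40 and >40 Gy), 2 × 4 = 8.

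**Maximum-dose reading.** The maximum dose is normally at or above the prescription, so this reading would not lower the line. As an illustration, assume prescription to the 80% line, a figure not in the documents. The line is then 0.5 × 50 / 0.8 = 31.25 Gy to 0.5 × 60 / 0.8 = 37.5 Gy. The >20–30 Gy band would be empty and >30–40 Gy truncated.

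**The case against.** The strongest reply is that the intent can be guessed. Three sections list low bands without a limit, 7.1 lists them too, and whole ribs are mapped with dose at each vertex. One parenthesis points the other way, and an analyst applying it would notice the empty bands at once. The band missing from 11.2.1 is probably an editing slip. This is fair, and it is why the point is one of consistency and not of hidden bias. It does not settle the text: 2.2.3 formally defines the treatment field by this line, so reading it as deliberate in 7.1 is reasonable.

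It is also true that, for the two lowest bands, literal use of 7.1 gives a missing result and not a rival estimate. Rival estimates arise mainly for >20–30 Gy.

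Three limits on precision stand:

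- Subsection length and dose gradient are not given, so the frequency of straddling is unknown. The case is very strong for 0–10 Gy and somewhat weaker for >10–20 Gy.
- Section 11.4 places its sizing assumption inside the treatment field. On a maximum-dose reading the line could exceed 30 Gy and clip the bottom of that region if the limit were applied there.
- Appendix O, the cortical thickness form, is not in the text available here and may show which bands are recorded. It would not remove the conflict between the four sections.

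**Conclusion.** The concern holds. Section 7.1 as written essentially empties 0–10 and >10–20 Gy and reduces >20–30 Gy to between 5 and 0 Gy of width. It conflicts with 2.2.1, 5.2.1 and 11.2.1. Separately, 11.2.1 omits a band that the other three sections list. Literal use of 7.1 and 11.2.1 together leaves two of five bands.

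This should be fixed, but its reach is limited to secondary objective 2.2.1. If the 50% refers to the prescribed dose, only results at 30 Gy or below are affected. On the same reading the line never exceeds 30 Gy, so the primary region is unchanged; 2.1.1, 5.1.1 and 11.1 in any case define it as 30 Gy or more with no isodose limit. A maximum-dose reading could only widen the problem.

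**What to change.** Reconcile the sections before the unblinding that Section 10.0 sets after all patients complete 12 months. Two edits are possible.

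1. **Preferred: drop the isodose limit from the cortical thickness banding in 7.1**, keeping it for chest wall pain and fracture. This agrees with 2.2.1, 5.2.1 and 11.2.1 and uses rib thickness and dose data already mapped. The cost is wording in 7.1 and 11.2.1 and a little more analysis.
2. **If only in-field bone is intended, delete 0–10 and >10–20 Gy from 2.2.1, 5.2.1, 7.1 and 11.2.1.** State that >20–30 Gy is truncated at the line and how straddling subsections are assigned. The cost is wording in four sections and loss of the low-dose comparison.

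Under either edit, add >20–30 Gy to 11.2.1 and state in one line which dose the 50% refers to. Neither edit requires a new scan or visit or changes treatment.
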